3.2 Study Endpoints

- To determine the sensitivity and specificity of iBE exams for the detection of clinically relevant breast lesions (defined as BIRADS 3-5 on imaging, and/or malignant on biopsy).
- To determine inter-rater reliability in the iBE production prototype.

4 Subject Selection

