4.3 Subject Recruitment and Screening

Subjects will be offered participation in the study during their visit to the Women’s Imaging Center by the PIs, [name], [name], and/or their designee. This study may recruit up to 1000 subjects. Patient’s will be eligible for study participation if they have a scheduled visit for the Women’s Imaging Center and have not previously participated in this study. The reason for the patient’s visit, screening or diagnostic, will not affect their eligibility. Diagnostic visits are included as it is necessary to ensure the accuracy of the iBE device’s ability to detect BIRADs 3-5. The iBE device was created to use as a screening tool to detect clinically relevant breast lesions, defined here as BIRADs 3-5, with the purpose of giving patients proper follow-up recommendations without causing unnecessary anxiety of avoidable diagnostic tests.

5 Study Procedures

Participants will be recruited from the Women’s Imaging Center who are scheduled to undergo screening or diagnostic imaging including biopsies. Subjects will have the study explained to them and given the consent form to review early in their imaging center visit. After the subjects have had time to review the consent, the PI or designee will answer all questions. If she/he agrees and signs the consent form, they will receive a signed copy to take home with them. All subjects must meet the inclusion and exclusion criteria. Consent will be obtained prior to any study-related activities.

The iBE evaluation will be performed by a trained individual who is blinded to the outcome of the radiology studies at the time the iBE is performed. The trained individual will be a healthcare worker with minimum education (or equivalence) to a licensed practical nurse (LPN) or an ultrasound tech. This is the target education level for the intended iBE operators. The selected healthcare worker will be trained by [name], MD to administer the iBE and clinical breast exams. The trainee will follow [name] during clinic hours for 1-2 days and trained for clinical breast exams, similar training to a medical student. The iBE training will mostly be software and instrument training by the leading iBE user in the United States, [name]. A minimum of two healthcare workers will be trained.

[figure not shown]

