The current pathway of breast lesion detection can be modified in this protocol in order to ascertain the accuracy of the iBE device illustrated in Scheme 1 below. The current pathway of breast lesion screening and detection begins with a screening mammogram or a diagnostic mammogram/ultrasound. If nothing is detected by mammogram or ultrasound then the pathway is complete and a follow-up recommendation is given. However, if something suspicious is detected by the initial mammogram then additional imaging is requested such as an ultrasound. If the additional ultrasound reveals something suspicious a biopsy maybe recommended for confirmation or if a benign finding is revealed a follow-up recommendation is be given. The addition of iBE screening will only modify the current pathway if the iBE exam returns a positive result when the initial mammogram provides a negative result. If this occurs a study provided ultrasound will be recommended and the ultrasound’s results will be used to verify the iBE positive result. If the ultrasound invalidates the iBE positive result, it will be deemed a false positive and the diagnostic tests are complete. However, if the ultrasound confirms the iBE’s result [name] and the radiologist will discuss if further diagnostic intervention (i.e. biopsy) is required. Data on the final disposition of the imaging, any biopsies and any follow up imaging to 18 months after participation will be recorded in the database.

Scheme 1: Current Algorithm with Integrated Study Pathway

Quantitative Data

Quantitative data from the test will be documented and analyzed for accuracy metrics.

The iBE device collects only compression measurements and stores these data on the mobile device. Compression data are recorded for our records and a copy is available to UELS via Dropbox, which is backed up online and offsite.

We know the data are captured accurately because a unique file gets created at the end of every scan in a specific folder inside the DELL tablet. The app gives the user a notification that the data were saved properly to the tablet at the end of each scan.

The data sent to the UELS database are identical to those on the tablet, as they are synced between the folder inside the tablet and Dropbox. This ensures that an exact copy of the files created at the site are sent to UELS. These files use a unique ID entered by the user and have no identifiable patient information.

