6.2 Statistical Methods

Data will be analyzed using contingency table methods, estimating the sensitivity and specificity of the device to correctly assign subjects to BIRADS 1, 2 versus BIRADS 3, 4, 5 categories. Sensitivity is calculated from contingency table counts as $TP/(TP+FN)$, and specificity is calculated as $TN/(TN+FP)$, (and will be log transformed) with variances obtained using the delta method. Both sensitivity and specificity measures are expected to be high, given great performance in preliminary data (0.95 and 0.92 respectively). We will use a non-inferiority approach, attempting to demonstrate that in the clinical setting, iBE matches our preliminary values, and we will test them against null hypothesis values (Non inferiority boundaries) that are 5% below our preliminary data using the z-score for the log-transformed measure.

	Mammogram BIRADS 1,2	Mammogram BIRADS 3,4,5 or biopsy positive (same breast and same quadrant)
iBE negative	True Negative (TN)	False Negative (FN)
iBE positive	False Positive (FP)	True Positive (TP)

And to CBE as a primary comparison

	CBE negative	CBE positive
iBE negative	True Negative	False Negative
iBE positive	False Positive	True Positive

7 Safety and Adverse Events

Due to the nature of this device and our experience thus far, adverse effects are not anticipated, however, the investigator will follow the processes below should an event occur.

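### Section 3.2 and the 6.2 table define a reference-positive subject differently, so the primary 2x2 table can be filled in two ways from the same data

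*Combined protocol and SAP*

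**What the plan says.** Combined protocol and SAP, by section:

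- **3.2 (endpoints):** the target is "clinically relevant breast lesions (defined as BIRADS 3-5 on imaging, and/or malignant on biopsy". It limits neither the imaging modality nor the location.
- **6.2 (first table):** the positive column is headed "Mammogram BIRADS 3,4,5 or biopsy positive (same breast and same quadrant" and the negative column is mammogram BIRADS 1 or 2. Ultrasound appears in neither.
- **6.2 (text above the table):** the device is to "correctly assign subjects to BIRADS 1, 2 versus BIRADS 3, 4, 5 categories". Section 4.3 similarly has the device "detect clinically relevant breast lesions, defined here as BIRADs 3-5". Neither names a modality or biopsy.
- **5 (procedures):** the usual pathway of "screening and detection begins with a screening mammogram or a diagnostic mammogram/ultrasound", so some subjects have ultrasound regardless of iBE. Adding iBE "will only modify the current pathway if the iBE exam returns a positive result when the initial mammogram provides a negative result". A study ultrasound then follows, and its "results will be used to verify the iBE positive result". Only for a scan that does not bear out the iBE finding does the text name a cell: "If the ultrasound invalidates the iBE positive result, it will be deemed a false positive and the diagnostic tests are complete". If the ultrasound confirms the finding, the text describes only a discussion about further work-up. Scheme 1, which illustrates the pathway, is not shown in the text available.
- **2 (objectives):** accuracy is to be established against mammography-based screening results.

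**The concern.** The reference standard determines every cell of the primary table. The two definitions disagree on subjects whose only BIRADS 3-5 finding is on ultrasound, and section 5 deliberately sends one such group to ultrasound. Two analysts following the plan could report different sensitivity and specificity from the same records, and the choice could be made after the data are seen.

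The choice is not neutral for iBE-triggered ultrasound. That scan follows only a positive iBE result, so counting it can turn false positives into true positives but can never reveal a lesion that iBE missed. It can only raise both estimates. Ultrasound scheduled independently of iBE has no such one-way effect, because it can also show lesions that iBE missed.

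**Working it through.** **Step 1. Apply both definitions to the same subjects.** All have mammogram BIRADS 1-2, ultrasound BIRADS 3-5 and no positive biopsy.

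| Subject | 3.2 | 6.2 table |
|---|---|---|
| iBE positive, iBE-triggered study ultrasound | TP | FP |
| iBE positive, scheduled ultrasound | TP | FP |
| iBE negative, scheduled ultrasound | FN | TN |

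**Step 2. Inputs.** Section 6.2 gives expected sensitivity 0.95 and specificity 0.92, boundaries 5% below, and a z-score on the log scale with delta-method variance. Section 6.1 gives 1000 subjects and 80% BIRADS 1-2 among screening mammograms.

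My assumptions are:
- 800 reference negatives and 200 positives under the table (enrichment would raise the positives);
- one count per subject;
- absolute boundaries of 0.87 and 0.90;
- one-sided 0.05;
- 0.92/0.95 as the values under the 6.2 table.

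The only stated design figure, 80% power, does not bear on this point.

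Formula: z = [ln(p) − ln(p0)] / sqrt[(1 − p)/(n·p)], pass if z > 1.645.

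Table rule: TP 190, FN 10, FP 64, TN 736.
- Specificity 736/800 = 0.920, z = 5.36.
- Sensitivity 190/200 = 0.950, z = 3.33.

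**Step 3. Effect of iBE-triggered ultrasound alone.** Move k subjects from FP to TP. Specificity = 736/(800 − k); sensitivity = (190 + k)/(200 + k).

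| k (assumed) | Specificity | Sensitivity |
|---|---|---|
| 10 | 736/790 = 0.932 | 200/210 = 0.952 |
| 20 | 736/780 = 0.944 | 210/220 = 0.955 |

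Both tests pass under either rule. To find where the rule decides the specificity test, take the smallest passing TN: 711 of 800 under the table, 702 of 790 for k = 10, and 693 of 780 for k = 20. The rule therefore decides the result only if the table shows:
- k = 10: TN of 702 to 710 of 800 (0.878 to 0.888);
- k = 20: TN of 693 to 710 of 800 (0.866 to 0.888).

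Example: 704/800 = 0.880 has z = 0.88 and fails; 704/780 = 0.903 has z = 3.12 and passes.

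**Step 4. Full 3.2 rule.** Lesions on scheduled ultrasound that iBE missed also move, from TN to FN. Keep k = 10 and assume m such misses. Sensitivity = 200/(210 + m); specificity = (736 − m)/(790 − m).

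| m (assumed) | Sensitivity | z against 0.90 | Specificity |
|---|---|---|---|
| 5 | 200/215 = 0.930 | 1.77, just passes | 731/785 = 0.931 |
| 10 | 200/220 = 0.909 | 0.47, fails | 726/780 = 0.931 |

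The table rule, on the same subjects, gives 0.950 and z = 3.33. Neither k nor m can be taken from the documents. The in vivo testing in section 1.6 is counted by lesion and gives no BIRADS category.

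**The case against.** The strongest reply is that the table header is merely loose. Sections 3.2 and 5 point the same way: ultrasound is there to verify iBE, and only an invalidated result is called a false positive. On that reading, the mammogram in the header stands for imaging in general, and correcting one header settles the matter. It stands that section 5 leans towards true positive and that this is a legitimate rule to adopt. But no visible text says the header is shorthand, section 2 leans towards the table, and section 5 neither names the cell for a confirmed result nor defines confirmation in BIRADS terms.

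It also stands that the size is hypothetical. The values of k and m are assumed, and at 0.92/0.95 the iBE-triggered ultrasound alone changes neither test result.

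A reader might go further in either direction:
- That the 3.2 rule always flatters the device. The documents do not support this: 3.2 covers all imaging, so scheduled-ultrasound misses count against iBE. The one-way effect belongs to iBE-triggered ultrasound only.
- That at the expected values the conflict cannot change a result, or barely touches sensitivity. That too holds only for iBE-triggered ultrasound; step 4 shows otherwise for the full rule.

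**Conclusion.** The contradiction is real and lies in the primary 2x2 table. It is conflicting text rather than missing detail, and should be resolved before analysis. The classification conflict in step 1 needs no numerical assumption.

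Its numerical effect is unknown. Under the stated assumptions, iBE-triggered ultrasound alone adds 1.2 or 2.4 points of specificity for k = 10 or 20, and matters to the test only when observed table specificity is near its boundary. Under the full 3.2 rule the sensitivity test can change even at the plan's expected values: it just passes with 5 assumed misses and fails with 10. These results also depend on the 800/200 split, the absolute margin and the one-sided 0.05 level, none of which the plan states.

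A reader might infer that the trial's conclusion will turn on this conflict, or that the rule will be picked to suit the data. The documents support neither. They leave the choice open and do not give the number of affected subjects.

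**What to change.** Before analysis, write one primary reference rule and use it unchanged in 3.2, section 5, the 6.2 text and the 6.2 table. Keep the same-breast, same-quadrant match, and say which cell an ultrasound-only BIRADS 3-5 lesion enters.

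- **Suggested primary rule:** BIRADS 3-5 on mammogram, or on ultrasound scheduled or prompted independently of iBE, or malignancy on biopsy, at the index work-up.
- **Data:** record what prompted each ultrasound.
- **Secondary analysis, labelled as such:** count lesions seen only on iBE-triggered ultrasound as true positives. If the sponsor prefers the section 5 reading as primary, swap the two analyses and state that counting these lesions can only raise both estimates.
- **18-month outcomes:** keep them as a sensitivity analysis. Section 5 records them, but neither definition uses them. Section 3.1 expects the primary analyses about 2 years from activation, so an 18-month window in the primary reference would leave roughly 24 − 18 = 6 months to enrol up to 1000 subjects.

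The cost is wording in four places, one CRF field and one extra analysis (the secondary), plus the 18-month sensitivity analysis on data already recorded. The statistical price is a primary specificity lower than if iBE-triggered lesions counted as true positives. The 1.2 and 2.4 points above indicate the order of size, but they compare with the table, not with the suggested rule. Sensitivity may also be lower than under the table, because scheduled-ultrasound lesions missed by iBE would now count.

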1.3 Health worker led “earlier detection”

The American Joint Committee on Cancer (AJCC) staging system indicates prognosis based on the size of the tumor at detection viz. stage of breast cancer. Identifying tumors at earlier stages (down-staging) can improve survival, assuming high-quality treatment is accessible. In the U.S., approximately 40 million women receive mammograms annually and roughly 232,000 new cases are identified; vast majority are detected at stage Tis and T1 with a 5-year survival of 100%. In the context of LMICs, where up to two-thirds of breast cancer cases present at late stages, systematic down-staging is required, such that majority of the cases would be identified at Stage II or earlier, where survival can be 93% or better (again, assuming treatment is available).

In LMICs, health workers, nurses and midwives represent the most affordable resource to bridge the accessibility gap due to the lack of secondary prevention programs like in HICs. What is needed is a low-cost, user-friendly technology that can be used by health workers with minimal training to administer standardized breast exams without any special infrastructure with the goal to down-stage breast cancer to at least Stage II. The low-cost technology must perform with better detection sensitivity than CBE (higher than 50%) and equally high specificity as CBE (94%) to accurately and effectively identify breast lumps in need of further diagnostic follow-up (diagnostic ultrasound, breast biopsy) without clogging the under-resourced infrastructure with false positives due to typical benign breast features (tissue variability, lumpiness and nodularity).

Contrast in elastic stiffness between normal and abnormal breast tissue has long been recognized (Harris '94). Breast cancers are known to be stiffer than normal breast tissues. Major medical device manufacturers are exploring different sensing mechanisms like Ultrasound Elastography and MRI, which use tissue stiffness to differentiate between malignant and non-malignant tissue.

[figure not shown]

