Subjects will be scanned with the iBE device administered by the trained individual while in a supine position without breast immobilization similar to ultrasound testing. A bilateral iBE exam will be performed on the entire breast as well as a bilateral Clinical Breast Exam (CBE) the findings will be documented on the case report forms and the device tablet concurrently.

If the patient is selected to participate in the inter-rater reliability portion of the study, the subject will undergo both the iBE and the clinical breast exams twice performed by two different separately trained individuals sequentially during the same visit. The trained individuals will have their own case report forms and tablets that integrate to the iBE to prevent results sharing and bias. The selection for the inter-rater reliability portion of the study will be decided by the day of the week. The second trained individual will be present one a day week and that day all the patients will be asked to participate in the dual exam inter-rater reliability portion of the study.

These data are recorded and processed by an automated software algorithm and the results are displayed topographically on a “breast-map” with red areas showing positive findings and green areas showing negative findings. All the recorded data are collected on the tablet without HIPAA identifying variables. The tablet will assign a four digit subject number incrementally increasing for each subject prior to the iBE scan and this number will be recorded on the case report form. Results of the test will be reported to the patient as well as the radiology technologist and radiologist. The iBE evaluation may add between 10 and 30 minutes to the clinic visit. The iBE evaluation will be done prior to the patient’s original scheduled imaging visit. After the completion of the imaging visit the radiologist will evaluate the images and the iBE report. If there are areas identified on the iBE that are not resolved by the scheduled mammogram an ultrasound will be performed in the area of concern (if not already scheduled).

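### The CBE table in section 6.2 treats CBE as the truth, so it counts confirmed lesions that CBE missed as iBE false positives and cannot show which exam is more sensitive

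*Combined protocol and SAP*

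**What the plan says.** Section 3.2 makes the sensitivity and specificity of iBE for relevant lesions an endpoint, a lesion being "defined as BIRADS 3-5 on imaging, and/or malignant on biopsy". CBE is not part of that definition.

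Section 6.2 gives two 2x2 tables. The positive column of the first is "Mammogram BIRADS 3,4,5 or biopsy positive (same breast and same quadrant"). The second is introduced by "And to CBE as a primary comparison". Its columns are CBE negative and CBE positive, and its cells carry the same labels as the first: iBE positive with CBE negative is a false positive, and iBE negative with CBE positive is a false negative. In the same section, "Sensitivity is calculated from contingency table counts as" TP/(TP+FN), and specificity as TN/(TN+FP). No hypothesis or margin is given for the CBE table.

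Two other places bear on this. Section 1.3, as background, says: "The low-cost technology must perform with better detection sensitivity than CBE (higher than 50%) and equally high specificity as CBE (94"%). Section 5 settles a disputed iBE positive by ultrasound, not by CBE.

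**The concern.** With those labels, CBE is the reference standard. An iBE finding that imaging or biopsy confirms but CBE missed is a true positive in the first table and a false positive in the second. A device can reach 100% on both measures in the second table only by agreeing with CBE on every subject, including where CBE is wrong.

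Two things are at stake. Percentages reported from this table as sensitivity and specificity would really be agreement with CBE. And the natural question of a comparison called primary, whether iBE detects more than CBE, would have no analysis able to answer it, because CBE is nowhere scored against imaging or biopsy.

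**Working it through.** The plan gives no figure for the CBE comparison, so there is none to reproduce. The 80% power in section 6.1 is not tied to any named comparison.

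**1. The labels side by side** (subject level, location matching ignored)

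| iBE | CBE | Imaging/biopsy | First table | CBE table |
|---|---|---|---|---|
| + | − | lesion | true positive | false positive |
| − | + | no lesion | true negative | false negative |
| + | + | no lesion | false positive | true positive |
| − | − | lesion | false negative | true negative |

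The two tables contradict each other in every case where CBE is wrong. This needs no numerical assumption.

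**2. The CBE table cannot rank the exams**

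Take 1000 subjects, 200 with lesions. Cells are in the order both positive / iBE only / CBE only / neither.

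| | Lesions | Non-lesions | Total |
|---|---|---|---|
| Scenario A | 95/95/5/5 | 4/60/44/692 | 99/155/49/697 |
| Scenario B | 95/10/45/50 | 4/145/4/647 | 99/155/49/697 |

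- A: iBE 190/200 = 95% and 736/800 = 92%; CBE 100/200 = 50% and 752/800 = 94%.
- B: iBE 105/200 = 52.5% and 651/800 = 81.4%; CBE 140/200 = 70% and 792/800 = 99%.

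Both scenarios report an iBE sensitivity of 99/148 = 66.9% and specificity of 697/852 = 81.8%.

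**3. Illustrative size**

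Inputs: 1000 subjects (section 6.1). iBE 0.95/0.92 (preliminary values, section 6.2). CBE 0.50/0.94 (figures in section 1.3, used as an example). Lesion share 20% is an assumption: section 6.1 puts 80% of screening mammograms in BIRADS 1 and 2 and does not quantify the enrichment.

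CBE positives: 200 × 0.50 + 800 × 0.06 = 148. CBE negatives: 852.

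*Exams independent given lesion status:*
- Lesions: 95/95/5/5. Non-lesions: 3.84/60.16/44.16/691.84.
- Apparent sensitivity (95 + 3.84)/148 = 66.8%; apparent specificity (5 + 691.84)/852 = 81.8%.
- False positives: 95 + 60.16 = 155.16, of which 95 are real lesions.

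*Maximal positive dependence:*
- Lesions: 100/90/0/10. Non-lesions: 48/16/0/736.
- Apparent sensitivity 148/148 = 100%; apparent specificity (10 + 736)/852 = 87.6%.
- False positives: 90 + 16 = 106, of which 90 are real lesions.

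*Flawless iBE:* 100/148 = 67.6% and 752/852 = 88.3%. *iBE identical to CBE:* 148/148 and 852/852, both 100%.

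Other inputs, from independence to maximal positive dependence:

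| Lesion share | CBE sensitivity | Apparent sensitivity | Apparent specificity |
|---|---|---|---|
| 20% | 0.50 | 66.8–100% | 81.8–87.6% |
| 20% | 0.70 | 72.8–100% | 85.6–91.9% |
| 50% | 0.50 | 85.7–100% | 61.8–67.4% |

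**4. Better detection lowers the score**

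Hold iBE specificity at 0.92 and raise its true sensitivity from 0.50 to 1.00, other inputs as in the base case. Under independence, apparent specificity falls from (50 + 691.84)/852 = 87.1% to 691.84/852 = 81.2%. Under maximal dependence it falls from (100 + 736)/852 = 98.1% to 736/852 = 86.4%.

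**The case against.** - **The first table also exists.** It separates scenarios A and B, and in A the two tables together do rank the exams. There, 64 of the 254 iBE positives have no lesion, so at least 99 − 64 = 35 and at most 99 + 10 = 109 lesions are CBE positive. CBE sensitivity is then 17.5–54.5%, below iBE's 95%. This stands, but it is not general: scenario B's margins allow 0 to 99 + 49 = 148 of 200, or 0–74%, around iBE's 52.5%. Nor is such bounding planned.
- **It may be only an agreement table with copied labels.** The text of section 6.2 does describe accuracy for BIRADS categories, and the CBE table hangs on a sentence fragment. But the labels, together with the formulas in the same section, give accuracy figures against CBE. If agreement is meant, the labels are wrong.
- **Superiority over CBE is not an endpoint.** Correct: section 1.3 is background, and section 3.2 lists no CBE comparison. That limits the weight. Section 6.2 nevertheless calls the comparison primary.
- **The figures are illustrative and the range is incomplete.** Also correct. Maximal negative dependence would give 90/148 = 60.8% and 688/852 = 80.8%. Steps 1 and 2 do not depend on these inputs.

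**Conclusion.** The concern holds. As written, the CBE table reports agreement with CBE under the names of accuracy measures, counts confirmed lesions that CBE missed against iBE, and cannot by itself say which exam is more sensitive. That follows from the cell labels and the lesion definition alone.

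The size depends on lesion share, CBE accuracy and the dependence between the exams, none of which the plan fixes for this comparison. In the base case, 95 of 155 to 90 of 106 nominal false positives would be real lesions. The listed accuracy endpoint, based on the first table, is not touched by this defect. It should be corrected before analysis; the data are not compromised.

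**What to change.** 1. **Score both exams against the same imaging/biopsy reference in the same subjects.** Compare sensitivity in reference-positive and specificity in reference-negative subjects, as paired differences with McNemar-type confidence intervals. Apply the same breast and quadrant rule to both. In the base case under independence this uses 95 against 5 discordant lesions: (95 − 5)/200 = 45 points, the true gap of 0.95 − 0.50.
2. **Keep the iBE-by-CBE table as an agreement table only**, without true/false labels. Do not assume the two results are independent: section 5 trains the health worker in both exams, so the same operator appears to perform both.
3. **State the reference.** Section 3.2 says imaging; the first table says mammogram. The choice decides whether an ultrasound-only finding counts.
4. **Add a sensitivity analysis for verification bias.** By section 5, the study pathway "will only modify the current pathway if the iBE exam returns a positive result when the initial mammogram provides a negative result", and "After the completion of the imaging visit the radiologist will evaluate the images and the iBE report". Repeat the comparison with the reference limited to scheduled imaging and biopsy, excluding iBE-triggered ultrasound, and report the bias that remains.

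The cost is SAP wording and some extra analysis. CBE is done alongside iBE, and imaging and biopsy outcomes are to be recorded, so no subjects or procedures are added. The sponsor should confirm that imaging results are captured for everyone, since one sentence on the case report form in section 5 names only symptomatic individuals.

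The drawback is a remaining tilt towards iBE. As an assumed example, suppose both exams detect 100 of 200 lesions and 10 more, all CBE negative, enter the reference only through iBE-triggered ultrasound. iBE then shows 110/210 = 52.4% and CBE 100/210 = 47.6%, a gap of 4.8 points. The sensitivity analysis removes that part, but not any influence of the iBE report on the imaging read.

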3.1 General Design

Determination of the accuracy of iBE for the detection of clinically relevant breast lesions will be performed by means of a prospective study. Subjects may participate during a previously scheduled visit to the women's imaging center. All women presenting to the imaging center, including screening, diagnostic or interventional procedures, will be eligible for participation. A subset of patients will undergo dual examinations by different trained individuals with the results compared for inter-rater reliability.

The estimated date for the investigators to complete this study (complete primary analyses) is approximately 2 years from study activation.

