4.1 Inclusion Criteria

- 18 years of age and older
- Women and men with symptomatic breast lump (either by palpation or imaging) OR
- Asymptomatic women presenting to the imaging center for a screening mammogram.
- Signed Informed Consent

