6.1 Sample Size Determination

Based on a study of BIRADS grading of a mammography registry, 80% of all screening mammograms are BIRADS 1 and 2. The incidence of malignancy should be 1-2% of all screening mammograms. The screening center performs 11,000 screening mammograms a year plus over 3000 biopsies. About 600 breast cancers are diagnosed yearly. Since symptomatic individuals scheduled to undergo diagnostic imaging or biopsy are eligible to participate this will enrich the population categorized to BIRADS 3-5. Using a sample size of 1000 subjects provides 80% power.

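### The primary iBE-versus-CBE comparison pools subjects whose lump was already known by palpation, so the sensitivity difference depends on an unrecorded enrolment mix and tends to understate any iBE advantage.

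*Combined protocol and SAP*

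**What the plan says.** Section 6.2 sets out two 2x2 tables. The first scores iBE against mammographic BIRADS category or biopsy. The second is introduced by "And to CBE as a primary comparison" and cross-classifies iBE with CBE, with CBE in the position of the truth. No hypothesis, margin, paired test or power is given for iBE versus CBE, and section 3.2 lists no CBE endpoint.

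There are two entry routes in section 4.1: "Women and men with symptomatic breast lump (either by palpation or imaging) OR" and "Asymptomatic women presenting to the imaging center for a screening mammogram". Section 3.1 is equally broad: "All women presenting to the imaging center, including screening, diagnostic or interventional procedures, will be eligible for participation". Section 6.1 makes the enrichment deliberate, saying of symptomatic subjects that "this will enrich the population categorized to BIRADS 3-5". It gives no expected share and no quota.

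Section 5 provides for a new bilateral CBE and a new bilateral iBE at the study visit. The examiner is blinded to the radiology outcome; blinding to the reason for referral or to a known lump is not stated. The data items listed there include age, bra size, BMI, lesion location and, for symptomatic subjects, imaging and pathology results. How the lump was first found is not among them.

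Section 1.3 gives the background aim: a technology more sensitive than CBE (figure given: 50%) and as specific (94%).

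**The concern.** CBE is palpation. A subject with a true lesion who came because someone had already felt a lump is more likely to be CBE-positive than a woman with a lesion and no known lump. Each such subject among the reference positives raises pooled CBE sensitivity and leaves iBE less room to do better. The pooled difference is then a weighted average, with weights set by whoever happens to enrol at this imaging center.

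The section 1.3 aim concerns health workers examining women in places without screening programs. The difference relevant to that aim is the one in women without a known palpable lump, and the plan provides no way to isolate it. A real iBE advantage could look small, and the pooled figure would not carry over to the international trial that section 2 says these results prepare for.

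**Working it through.** **The plan's own figure.** Section 6.1 states 80% power with 1000 subjects. It names no test, alpha or number of positives, so the figure cannot be uniquely reproduced. The margins in section 6.2 are set against preliminary iBE values, not against CBE, so no stated power applies to the CBE comparison.

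**Formula.** Let w be the share of reference-positive subjects who entered with a palpated lump, D0 the iBE-minus-CBE sensitivity difference in the other positives, and D1 the difference in palpable-lump referrals. The pooled difference is

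D(w) = (1 − w)·D0 + w·D1,

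which is smaller than D0 whenever D1 < D0.

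**Inputs.** CBE 0.50 is the section 1.3 figure, and 0.32 is the middle of the 28-36% range in section 1.2. The remaining inputs are assumptions: iBE 0.80 in lesions not found by palpation, both exams 0.95 in palpable-lump referrals (so D1 = 0), and w itself.

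| w | iBE pooled | CBE pooled (base 0.50) | Difference | Difference with CBE base 0.32 |
|---|---|---|---|---|
| 0 | 0.80 | 0.50 | 30 points | 48 points |
| 0.25 | 0.8375 | 0.6125 | 22.5 | 36 |
| 0.50 | 0.875 | 0.725 | 15 | 24 |
| 0.75 | 0.9125 | 0.8375 | 7.5 | 12 |

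Example at w = 0.50: iBE 0.5 × 0.80 + 0.5 × 0.95 = 0.875; CBE 0.5 × 0.50 + 0.5 × 0.95 = 0.725; difference 0.15.

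**Sensitivity to the assumptions.** Hold iBE at the section 6.2 value of 0.95 throughout, and let r be the proportion of palpable-lump referrals with a true lesion who are positive on the study CBE. The lead is 0.95 − [w·r + (1 − w)·0.50].

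- r = 1.0: 45, 32.5, 20 and 7.5 points at w = 0, 0.25, 0.50 and 0.75.
- r = 0.8: 45, 37.5, 30 and 22.5 points.

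The direction is the same in both models, but the size changes a good deal.

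**Specificity.** The same weighted average applies among BIRADS 1-2 subjects. Benign palpable lumps can make CBE positive, but section 1.4 describes iBE as an electronic form of palpation that also detects benign growths. If both exams flag these lumps equally often, both specificities fall together and the difference in that stratum is zero. If one flags them more often, the shift goes against that one. The documents do not say which.

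**The second table as written.** Assume 20% of subjects are reference-positive and CBE is 50% sensitive and 94% specific. A perfect iBE would score:

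- sensitivity 0.2 × 0.50 / (0.2 × 0.50 + 0.8 × 0.06) = 0.100 / 0.148 = 67.6%;
- specificity 0.8 × 0.94 / (0.2 × 0.50 + 0.8 × 0.94) = 0.752 / 0.852 = 88.3%.

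This happens with no palpation selection at all. Both exams must be scored against imaging/biopsy before the enrolment mix can be addressed.

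**Precision within a stratum.** Exact two-sided 5% McNemar power for 0.80 versus 0.50, with discordant probabilities 0.40/0.10 (independent exams) and 0.35/0.05 (positively correlated exams):

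| Positives without a known palpable lump | Power |
|---|---|
| 100 | at least 0.99 |
| 50 | 0.84-0.94 |
| 30 | 0.59-0.71 |
| 20 | 0.37-0.45 |

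**The case against.** A reader might infer that the comparison is selected on CBE's own result and therefore cannot fairly show whether iBE beats CBE. The documents do not support either part. The qualifying palpation took place before the visit, by an unspecified person, while the study CBE is a new exam by a newly trained worker, and nobody enters on its result. Asymptomatic and imaging-detected subjects are not selected on palpation at all. On sensitivity the distortion generally runs against iBE, so an observed lead would be conservative. With 200 reference positives (an assumption: 20% of 1000), the first set of sensitivities above and independent exams, pooled McNemar power is above 0.99, 0.98 and 0.62 at w = 0.25, 0.50 and 0.75. Only the largest assumed share does serious harm to power, and nothing in the documents points to it.

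A reader might also infer that the specificity difference is pushed in iBE's favour. That would require iBE to ignore benign lumps that CBE feels, which no section states.

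Three further points stand. Enrichment is deliberate and explained in sections 4.3 and 6.1. Section 1.3 is background rather than a hypothesis of this study. The more basic fault is that the second table treats CBE as the truth. None of this removes the point: correcting that table would leave a pooled difference that depends on the enrolment mix, and the listed data would not allow it to be separated.

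**Conclusion.** The point holds in limited form. CBE is called a primary comparison, prior palpation is an entry route, and nothing planned separates those subjects. Pooled CBE sensitivity is likely raised, and the pooled difference tends to understate any iBE advantage in women without a known palpable lump.

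Under the first set of assumptions, half or a quarter of a 30-point difference remains when 50% or 75% of positives are palpable-lump referrals. The size is unknown because the documents give neither the share nor the stratum sensitivities. The direction rests on the iBE-minus-CBE difference being smaller in palpable lumps than elsewhere, which is plausible but not documented. No direction can be claimed for specificity. The comparison with the BIRADS/biopsy reference in the first table of section 6.2 is not the subject of this point. This is a cheap improvement, not a defect that invalidates the study.

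**What to change.** - In section 6.2, score iBE and CBE each against the imaging/biopsy reference and compare them as paired proportions (McNemar), in place of the table that uses CBE as the truth.
- Pre-specify this comparison stratified by whether a lump was known by palpation before the visit. Give the stratum without a known palpable lump as the estimate relevant to the section 1.3 aim, alongside the pooled result.
- Add one CRF item, lump known by palpation before this visit (yes/no), completed by recruiting staff and not shown to the examiner.
- Track the number of reference positives without a known palpable lump during enrolment.

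The cost is SAP wording, one tick box and less precision within strata. No subject is excluded. Restricting the main comparison to one stratum and demoting the pooled result is not needed, and would be risky if only 20 or 30 such positives enrol, as the power table shows.
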